## 2. Objectives, Endpoints and Hypotheses

### 2.1 Objectives and Endpoints/Estimands

Objectives	Endpoints
Primary	

To evaluate the effect of efavaleukin alfa on induction of clinical remission

	

Clinical remission at week 12

Primary Estimand	
Variable: Clinical remission at week 12	
Estimator: Difference in clinical remission rates	
Population: All subjects with moderately to severely active UC with inadequate response, loss of response, or intolerance to at least 1 of the following: conventional therapy, biologics, or targeted small molecules, who are randomized and received at least 1 dose of investigational product.	
Treatments: Each efavaleukin alfa dose group and placebo.	
Intercurrent event – composite variable strategy: Subjects will be considered as not meeting the endpoint if:	

They initiate or increase the dose of UC related protocol-prohibited medication or concomitant UC medication between the date of the screening endoscopy and the week 12 endoscopy.

Discontinuation of investigational product on or prior to the end of induction period.

A colectomy (partial or total) or an ostomy.

	
Secondary	

To evaluate the effect of efavaleukin alfa on induction of clinical response

	

Clinical response at week 12

To evaluate the effect of efavaleukin alfa on induction of endoscopic remission

	

Endoscopic remission at week 12

• To evaluate the effect of efavaleukin alfa on induction of symptomatic remission

	

• Symptomatic remission at week 12

• To evaluate the effect of efavaleukin alfa as induction therapy on combined endoscopic and histologic remission

	

• Combined endoscopic remission and histologic remission of the colon tissue at week 12

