**Completion of IP in the induction period:**

A subject will be considered as completing IP in the induction period if they do not discontinue IP prior to the **end of the induction period**. A subject will be considered as completing IP in the long-term treatment period if the End of IP reason is “Completed” on the End of IP eCRF.

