**5.3 Study Dates**

**End of Induction Date:**

End of Induction date for each subject is defined as date of the week 12 endoscopy. For subjects who discontinued from the study before completing the week 12 visit, or did not have a week 12 endoscopy, the end of induction date will be min(Study Day 90, EOS).

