### **9.2 Subject Accountability**

The number and percent of subjects who were randomized, received investigational product in the induction period, discontinued investigational product in the induction period (including reasons for discontinuing), completed investigational product in the induction period, and completed the induction period will be summarized overall and by randomized treatment group.

The number and percent of subjects who completed investigational product for the overall study, discontinued investigational product at any time during the study (including reasons for discontinuing), and overall study completion (defined as completed study on the eCRF) will be summarized overall, by randomized treatment group, and week 12 response status (subjects randomized to placebo only).

Summary of subjects who discontinue investigational product/study due to COVID-19 control measures will be included.

Key study dates for the first subject enrolled, last subject enrolled, last subject's end of investigational product, and last subject's EOS will be presented.

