#### **9.5.2 Analyses of Primary Efficacy Endpoint(s)/Estimand(s)**

The primary analysis of the primary efficacy estimand will use the logistic regression model described in [Section 9.5.1.1](#) based on the Full Analysis Set (FAS) described in [Section 6.1](#) and the subjects with missing data will be imputed using nonresponder imputation.

A composite variable strategy will be used to handle intercurrent events for the primary estimand. Subjects will be considered as not meeting the endpoint if they meet any of the following criteria:

- Initiation of or **increase the dose of UC related** protocol-prohibited medication or concomitant UC medication **between the date of the screening endoscopy and the week 12 endoscopy**
- **UC related protocol-prohibited medications include:**
  - **Any investigational therapy for Ulcerative Colitis**

- **Biologic agents (eg, Vedolizumab, Ustekinumab, Infliximab, Adalimumab, Golimumab)**
- **T cell depleting agents (eg, Antithymocyte immunoglobulin, Campath [Alemtuzumab])**
- **Recombinant IL-2 (eg, Proleukin [aldesleukin])**
- **Jak Inhibitors (eg, Baricitinib, Tofacitinib, Upadacitinib)**
- **Other immunomodulatory agents (eg, S1P modulators [Fingolimod and siponimod], cyclosporine, Mycophenolic acid, tacrolimus, sirolimus)**
- **Corticosteroids via IV, intramuscular, or rectal route**
- **5-ASAs via rectal route**
- **Concomitant UC medication includes:**
  - **Oral 5-ASA**
  - **Immunomodulators (azathioprine, 6-mercaptopurine, methotrexate)**
  - **Oral corticosteroids**
- Discontinuation of investigational product on or prior to the **end of the induction period**

To assess the impact of the composite variable strategy for the intercurrent events, an additional analysis will be performed using the treatment policy strategy. In this analysis the actual remission status at week 12 will be used, regardless of each intercurrent event. Subjects with missing week 12 remission status will be imputed using nonresponder imputation.

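### A treatment stop dated on the day of the week 12 endoscopy and visit is a failure in SAP 2.1 and 9.5.2, a completed induction course in SAP 5.1, and no event under the protocol

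*SAP*

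**What the plan says.** **Protocol.** The primary estimand (Synopsis and Section 3) treats discontinuation of investigational product as failure only if it occurs before the week 12 visit. Sections 4.1.2 and 5.5 make treatment beyond week 12 optional. It is open to subjects who completed week 12, have not discontinued, and may benefit in the investigator's opinion.

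**SAP, efficacy rule.** Section 2.1 counts as failure "Discontinuation of investigational product on or prior to the end of induction period". Section 9.5.2 repeats the inclusive form: "Discontinuation of investigational product on or prior to the" end of the induction period.

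**SAP, anchor date.** Section 5.3 says "End of Induction date for each subject is defined as date of the week 12 endoscopy". For a subject who left before completing the week 12 visit, or had no such endoscopy, it is the earlier of study day 90 and the end-of-study (EOS) date.

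**SAP, disposition rule.** Section 5.1 sets a strict inequality against that same anchor: "A subject will be considered as completing IP in the induction period if they do not discontinue IP prior to the", with the anchor named next. The long-term rule beside it works differently: "A subject will be considered as completing IP in the long-term treatment period if the End of IP reason is" recorded as completed on the end-of-treatment form. Section 9.2 then tabulates subjects who "completed investigational product in the induction period".

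**SAP, additional analysis.** Section 9.5.2 plans a treatment-policy analysis of the primary endpoint: "In this analysis the actual remission status at week 12 will be used, regardless of each intercurrent event". Section 9.5.3 applies the composite rule to the secondary endpoints and plans no such counterpart.

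**The concern.** The efficacy rule and the disposition rule share an anchor date but use opposite inequalities. A stop dated on the anchor day therefore falls on both sides. The protocol uses a different anchor, the visit, with a strict inequality.

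The endoscopy day is not an arbitrary date. Endoscopy is a week 12 visit procedure, and week 12 is when investigator and subject decide whether to continue. A subject who finishes induction in remission and does not go on could well have treatment recorded as ended that day. The SAP would overwrite an observed remission with failure, report the same subject as having completed induction treatment, and depart from the protocol's estimand.

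Without an endoscopy the error runs the other way. The strict wording in SAP 5.1 lets an early dropout count as a completer when treatment and study end on the same day.

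**Working it through.** The plan states no figure on this point, so the check is of the rules themselves.

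**Inputs.** s = recorded day of the treatment stop; V = day of the week 12 visit (nominally 85, window ±5, Protocol Table 1-2); E = day of the week 12 endoscopy; D = min(90, EOS day) if there is no endoscopy (SAP 5.3).

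**Rules as written.**
- Protocol event: s < V.
- SAP 2.1 and 9.5.2 failure: s ≤ E (or s ≤ D).
- SAP 5.1 completer: not (s < E) (or not (s < D)).

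| V | E or D | s | Protocol event | SAP failure | SAP 5.1 completer |
|---|---|---|---|---|---|
| 85 | E = 85 | 84 | yes | yes | no |
| 85 | E = 85 | 85 | **no** | **yes** | **yes** |
| 85 | E = 85 | 86 | no | no | yes |
| 85 | E = 88 | 86 | no | yes | no |
| 85 | E = 83 | 84 | yes | no | yes |
| none | D = min(90, 40) = 40 | 40 | yes | **yes** | **yes** |

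*Within the SAP*, the two rules conflict only when s equals the anchor date.

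*Against the protocol*, the result depends on date order. With E on or after V, the SAP failure rule is wider. With E one day earlier (E = 84, V = 85), s ≤ 84 and s < 85 are the same rule. With E two or more days earlier, the SAP rule is narrower.

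**Which date is s?** The SAP does not say whether it is the last dose, the decision or the date on the end-of-treatment form. Protocol Table 1-2 makes the week 12 dose the first long-term dose. If doses are 14 days apart (an assumption, taken from the 14-day window in the SAP 5.1 exposure definitions), induction doses fall on days 1, 15, 29, 43, 57 and 71. For a subject who took all six and did not continue, with V = E = 85:
- s = 71 (last dose): 71 < 85, so all three rules treat the subject as having discontinued.
- s = 85 (visit): SAP failure, SAP 5.1 completer, no protocol event.

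**Size per subject.** One recoded remitter shifts an arm's rate by 1/n. At the planned n = 60 this is 1/60 = 1.67, or 1.7 percentage points. Analysed arms may differ, because the study was terminated and one site is excluded. At an assumed 50 or 40 per arm the shift is 1/50 = 2.0 or 1/40 = 2.5 points.

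**The case against.** The best defence is that the inclusive rule is deliberate. SAP 5.3 starts the long-term period on the day after the end of induction, so the endoscopy day is the last day of induction and a stop that day belongs to it. On this view SAP 5.1 is the outlier, it serves only disposition tables, and making it inclusive is a one-place edit. That would remove the conflict inside the SAP and correct the day-40 case. It would still fail a subject who stops on the day of the endoscopy and visit, whom the protocol does not count, so the main problem would remain.

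Several limiting points stand:
- With an endoscopy, the conflict inside the SAP covers one calendar day, and for a binary endpoint it matters only for a subject who otherwise met it.
- The rule is the same in every arm, and nothing in the documents shows a differential effect.
- The case report form is not among the documents, so the missing stop date is shown only for the SAP text. Taken alone it is missing detail.
- The protocol's wording on entry to the long-term period suggests that declining it differs from discontinuing, but does not say so.

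A reader might infer that the change of cut-off was concealed. The documents do not support that: the SAP version history for v3.0 records that the intercurrent-event definition was clarified. The fair criticism is that this entry does not name the new cut-off and that SAP Section 11 does not list it.

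**Conclusion.** The contradiction is real and worth correcting. Followed as written, the rules misclassify two kinds of subject: one who stops on the day of the week 12 endoscopy and visit (failure against the protocol, completer for disposition), and one without an endoscopy whose stop and end of study coincide before day 90 (dropout counted as completer). This reads the end of the induction period as the End of Induction date in SAP 5.3, the only definition given.

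The size is 1.7 points per affected remitter in a planned arm of 60. The number of such subjects, and so the direction and size of any bias, cannot be derived from the documents. The treatment-policy analysis of the primary endpoint does not depend on the rule; the secondary endpoints have no such check. The second kind of subject mainly affects disposition, since clinical remission needs an endoscopy subscore and SAP 8.3 already scores a missing one as failure.

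Two stronger readings are tempting. One is that the SAP rule is always stricter than the protocol's; the date cases show it can be wider, identical or narrower. The other is that the primary result is materially distorted, or that everyone who declines the long-term period is failed. Neither follows, because the documents give no count of affected subjects and do not say what stop date such a subject receives.

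**What to change.** 1. For subjects with a week 12 endoscopy, use one rule in SAP 2.1, 9.5.2 and 5.1: treatment discontinued before the week 12 endoscopy date. This matches the protocol's strict inequality.
2. For subjects without one, use on or before min(study day 90, EOS) in all three places.
3. Name the recorded date that marks a treatment stop.
4. State that finishing the scheduled induction doses without entering the optional long-term period is not an intercurrent event.
5. List the move from visit to endoscopy as anchor in SAP Section 11.

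**Check of the new rules.** With E = V = 85 and s = 85, 85 < 85 is false, so the subject is not a failure, is a completer and has no protocol event: all agree. With D = 40 and s = 40, 40 ≤ 40 is true, so the subject is a failure and not a completer.

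Differences from the protocol remain when endoscopy and visit fall on different days. With V = 85, E = 84 and s = 84, for example, the protocol counts an event and the new rule does not. That is why item 5 is needed.

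**Cost.** Wording in three places, one derivation and one line in Section 11; no new data and no change to the analysis sets. The drawback is timing. SAP v3.0 is dated 19 February 2025 and the third interim analysis that led to termination was in August 2024, so the edit must be documented as made after the termination decision. Treatment-policy analyses of the secondary endpoints would be a useful but optional addition.

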## Phase 2 Induction Period

Exploratory	

• To explore the effect of efavaleukin alfa as induction therapy on calprotectin levels in fecal samples

	

• Change from baseline in fecal calprotectin at week 12

• To explore efavaleukin alfa immunogenicity

	

• Anti-efavaleukin alfa antibodies and crossreactivity with IL-2

• Anti-efavaleukin alfa and anti-IL-2 neutralizing antibodies

IL-2 = interleukin-2.

## Long-term Treatment Period

Exploratory	

• To explore efavaleukin alfa immunogenicity during long-term treatment

	

• Anti-efavaleukin alfa antibodies and crossreactivity with IL-2

• Anti-efavaleukin alfa and anti-IL-2 neutralizing antibodies

IL-2 = interleukin-2.

## 2.2 Hypotheses and/or Estimations

The primary hypothesis is that at least 1 efavaleukin alfa dose will have greater efficacy compared to placebo as measured by clinical remission rate at week 12 in subjects with moderately to severely active UC.

### 3. Study Overview

#### 3.1 Study Design

This phase 2 dose-finding study is a multicenter, randomized, double-blind, placebo-controlled, parallel-group, 12-week induction study of efavaleukin alfa in subjects with moderately to severely active UC who have failed at least 1 of the following: conventional therapy (eg, immunomodulators, corticosteroids), biologic therapy, or targeted small molecule. This study will be used to establish the efavaleukin alfa induction dose and maintenance dose/dosing regimens for continued development. Subjects who complete the 12-week induction period will have the option to be treated in an exploratory long-term treatment period for up to 40 additional weeks if in the opinion of the investigator they may benefit from continued treatment. The primary analysis will occur after all subjects have had the opportunity to complete the week 12 visit. All primary and secondary objectives will be evaluated at the primary analysis.

#### Induction Period

Approximately **240** subjects will be assigned in a 1:1:1:1 ratio to placebo or 1 of 3 efavaleukin alfa dose parallel groups (n = **60** per group) as follows:

- Placebo [REDACTED]
- [REDACTED] µg [REDACTED]
- [REDACTED] µg [REDACTED]
- [REDACTED] µg [REDACTED]

Randomization will be stratified by prior experience with at least 1 biologic or targeted small molecule (yes/no) and corticosteroid use at randomization (yes/no). A maximum of 30% of enrolled subjects are allowed to be naïve to biologic or targeted small molecule therapy.

Clinical remission and clinical response will be assessed at the end of the 12-week induction period by the modified Mayo score using centrally read endoscopy subscore  
Interim analyses will be performed to assess futility.

An independent Data Monitoring Committee (DMC) will oversee safety and overall conduct of the study. The first 2 DMC meetings will occur after the first 20 subjects randomized have had the opportunity to complete the [REDACTED] and week 12 visits. Thereafter the DMC will plan to meet approximately every 3 months until Amgen is unblinded at the primary analysis. After Amgen is unblinded, the DMC will plan to meet

every 6 months. Ad hoc meetings can be scheduled as needed. The DMC will also review all available safety and efficacy data for interim analyses.

#### **Long-term Treatment Period**

Subjects who complete the safety and efficacy evaluations at week 12, have not discontinued investigational product, and who in the opinion of the investigator may benefit from continued treatment, will have the option to continue treatment in an exploratory long-term treatment period. The long-term treatment period will provide opportunity to explore the long-term safety and efficacy of continued treatment with efavaleukin alfa for up to 40 weeks (total of up to 52 weeks of treatment). During the long-term treatment period, subjects will continue to receive their assigned blinded dose of investigational product (placebo or efavaleukin alfa) at the week 12 visit. The exception will be placebo nonresponder subjects, who are defined as those randomized to placebo during the induction period and who failed to achieve clinical response at week 12. These placebo nonresponder subjects will be assigned in a blinded manner to receive [REDACTED] µg [REDACTED] dose during the long-term treatment period. Treatment assignment during the long-term treatment period will be done by interactive response technology (IRT) based on the modified Mayo score using the locally read endoscopy subscore assigned by the investigator.

During the long term treatment period, subjects will be assessed for worsening of disease activity, defined by a partial Mayo score of  $\geq 4$  with an increase from week 12 in rectal bleeding subscore to  $\geq 2$  and/or an increase from week 12 in stool frequency subscore to  $\geq 2$ . It is recommended that the investigator should determine whether a subject should discontinue investigational product based on worsening of disease activity, either based on the partial Mayo criteria above or their clinical judgement.

Subjects who were nonresponders at week 12, and who have an inadequate response by [REDACTED] will be discontinued from further investigational product administration in long-term treatment period.

Inadequate response is defined by failure to achieve a 2-point reduction and 25% improvement in partial Mayo score compared to the partial Mayo score at screening (and a minimum partial Mayo score of  $\geq 5$  points) at [REDACTED].

Efficacy evaluations during the long-term treatment period will include the total and partial Mayo score, fecal calprotectin, and corticosteroid use. The modified Mayo score

(including endoscopy) and mucosal biopsies for histopathology will be assessed at week 52/early termination visit.

If a subject discontinues investigational product prior to week 52, the subject will be encouraged to maintain the planned scheduled assessments through week 52. If the subject discontinues the study completely prior to week 52, the subject should complete an early termination (ET) visit (ie, week 52 visit procedures) which must be scheduled to allow for [REDACTED]

[REDACTED] who complete the week 52 endoscopy and who, in the opinion of the investigator, may benefit from continued treatment, will be assessed for eligibility to roll over into the Phase 2 Long Term Extension Study (20210210).

[REDACTED]

### 3.2 Sample Size

The planned sample size of **240** subjects provides approximately [REDACTED]

[REDACTED]

### 3.3 Adaptive Design

Interim analyses will be conducted to assess for futility. [REDACTED]

[REDACTED]. Futility will be assessed at each interim.  
[\(Section 7.1\).](#)

The interim analyses will be conducted by an external Independent Biostatistics Group (IBG) and results evaluated by an independent DMC. In the case where pre specified decision rules are met at a planned interim analysis, a Data Access Plan (DAP) Team will be invoked. The DAP Team is comprised of a small team of senior members internal to Amgen but external to the study team. To facilitate final decision making, the DAP Team may evaluate unblinded results. Further details will be described in a Data Access Plan.

The study team, investigators and subjects will remain blinded to the results of the IAs unless the DAP team have made the decision to terminate the trial.

#### **4. Covariates and Subgroups**

##### **4.1 Planned Covariates**

The analysis of the primary endpoint will include randomization stratification factors [prior experience with at least 1 biologic or targeted small molecule (Yes/No), corticosteroid use at randomization (Yes/No)] from the interactive response technology (IRT) system as main covariates in the model.

##### **4.2 Subgroups**

No subgroup analysis is planned for the final analysis of the study.

#### **5. Definitions**

##### **5.1 Basic Definition**

##### **Investigational Product (IP):**

The term investigational product is used in reference to efavaleukin alfa and placebo.

##### **Enrollment/Randomization Date:**

The enrollment/randomization date is the date on which a subject is assigned to a treatment group at the start of the induction period by the IRT system.

##### **First Dose Date:**

The first dose date is the date of administration of the first dose of IP; this may or may not be the same as randomization date.

##### **Placebo Nonresponder:**

A subject randomized to placebo who has not achieved clinical response by week 12.

##### **Placebo Responder:**

A subject randomized to placebo who achieves clinical response at week 12.

**Actual Treatment Received in the Induction Period:**

The actual treatment received in the induction period is the IP the subject actually received up to the end of induction date, regardless of what the subject was randomized to. In cases where a subject received both efavaleukin alfa and placebo, the actual treatment received will be the efavaleukin alfa dose. In cases where a subject received multiple efavaleukin alfa doses, the actual treatment received will be based on the maximum of efavaleukin alfa doses received. **In cases where a subject received an efavaleukin alfa dose higher than the highest dose specified in the protocol, the actual treatment received will be the highest dose.**

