**Duration of Induction Period IP Exposure:**

The duration of induction period IP exposure will be derived as the last date of IP administration prior to the week 12 endoscopy (or prior to EOS for subjects who do not have a week 12 endoscopy) plus 13 days (14 day window - 1), the day of first IP administration after the week 12 endoscopy - 1, EOS, or data cutoff date, whichever occurs first, minus the day of first IP administration + 1 day.

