**Duration of Long-term Treatment Period IP Exposure:**

The duration of long-term treatment period IP exposure for subjects who receive at least one dose of IP in the long-term treatment period will be derived as the last date of IP administration plus 13 days (14 day window - 1), EOS, or data cutoff date, whichever occurs first, minus the day of first IP administration after the [REDACTED] endoscopy +1 day.

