**Start of Long-Term Follow-Up treatment period:**

For subjects who continue into the long-term follow-up period, the start date is defined as the end of induction date plus one day.

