### Appendix B. Analytical Windows

Since the actual visit for a subject may not exactly coincide with their scheduled visit date, to allow for variations in scheduling, the following visit windows will be used to assign evaluations to a most appropriate nominal visit for analysis and summarization. Furthermore, there will be no gaps between visit windows in order to include as many data points as possible for summarization.

If more than one actual visit (including the unscheduled visits) falls within the same defined window, the visit closest to the target day with non-missing data will be considered for analysis. If two actual visit dates are at the same distance from the target day, the latest visit with non-missing data will be considered for analysis.

If more than one evaluation falls on the same date and time for laboratory results, then the value with the smallest accession number will be used.

Analysis visit windows for selected assessments are included in tables below. For remaining assessments, no visit window will be applied.

Study Day Window				
Analysis Visit	Target Day	Vital Signs	Chemistry, Hematology, Urinalysis	Fecal Calprotectin, hsCRP
6 to 24 hour Post Dose	1	1-2		
48 to 96 hour Post Dose	3	3 - 5		
		6 - 19	2 - 22 (Chemistry and Hematology only)	
		20 - 26		
		27 - 35	23 - 42 (Chemistry and Hematology) 2 - 42 (Urinalysis)	2 - 42
		36 - 49		
		50 - 63	43 - 70	43 - 70
		64 - 77		

	78 - end of induction date	71 - end of induction date	71 - end of induction date
	(end of induction date + 1) - 105		
106 - 119		(end of induction date + 1) - 126	
120 - 133			
134 - 147		127 - 154	
148 - 161			
162 - 175		155-182	(end of induction date + 1) - 210 (Fecal Calprotectin only)
176 - 189			
190 - 203		183-210	
204 - 217			
218 - 231		211-238	
232 - 245			
246 - 259		239-266	211 - 308 (Fecal Calprotectin only)
260 - 273			
274 - 287			
288 - 301			
302 - 315			
316 - 329			
330 - 343			

	344 - 357		
	358 - 378	267-378	309 - 378 (Fecal Calprotectin only)

Analysis Visit	Target Day	Study Day Window			
		Anti-efavaleukin alfa antibody	Partial Mayo Score, Physician Global Assesment (PGA)	Lymphocyte subset	Weight, Modified Mayo Score, endoscopy and Geboes score
	2 - 22	2 - 19	2 - 19		
		20 - 26	20 - 26		
	23 - 42	27 - 35			
		36 - 49	27 - 49		
	43 - 70	50 - 63			
		64 - 77			
	71 - end of induction date	78 - end of induction date	50 - end of induction date	2 - end of induction date	
		(end of induction date + 1) - 126			
		127 - 154			

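### A placebo nonresponder given the first long-term efavaleukin dose on the week 12 endoscopy day is labelled efavaleukin for the whole induction period in the safety tables

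*SAP*

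**What the plan says.** **Treatment label.** In SAP Section 5.1, a subject's actual induction treatment "is the IP the subject actually received up to the end of induction date, regardless of what the subject was randomized to". The mixed-treatment rule follows: "In cases where a subject received both efavaleukin alfa and placebo, the actual treatment received will be the efavaleukin alfa dose".

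**Period boundary.** SAP Section 5.3: "End of Induction date for each subject is defined as date of the week 12 endoscopy". Without a week 12 endoscopy, the date is the earlier of study day 90 and end of study. For subjects who continue, "the start date is defined as the end of induction date plus one day". In SAP Appendix B the post-induction windows also open on the day after that date.

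**Exposure.** SAP Section 5.1 bases induction exposure on "the last date of IP administration prior to the week 12 endoscopy" and caps it at "the day of first IP administration after the week 12 endoscopy - 1". The long-term definition of actual treatment takes product from week 12 onward. The overall-study groups combine the two labels, and one listed group is placebo in induction followed by AMG 592 long term.

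**Dosing.** Protocol Table 1-2 (footnote f) and Sections 6.1.1 and 6.1.1.2 place the first long-term dose at the week 12 visit, with up to 3 further days so that it can be given apart from the endoscopy. Text next to that window is blacked out. Section 8.1.2 puts dosing after the visit's other procedures. Placebo nonresponders switch to one efavaleukin dose, assigned on the local endoscopy read (Sections 4.1.2 and 6.1.1.2).

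**The concern.** The week 12 dose is the first dose of the long-term period, but the label rule closes induction at the end of the endoscopy day. If both fall on one day, a single efavaleukin dose at the very end relabels about 12 weeks of placebo.

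The label drives the safety tables:

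- SAP Section 9.6.1 presents induction adverse events by actual treatment received in induction, so the subject and any placebo-period events leave the placebo column and enter an efavaleukin column.
- Section 9.6.7 summarises exposure by arm and period. On the safety analysis set (Section 6.2), placebo exposure would appear under efavaleukin.
- The overall exposure-adjusted rates count time from the first dose of any product. Because the long-term definition can claim the same dose, both labels become efavaleukin, and the subject falls into an AMG 592 overall group instead of the placebo-then-AMG 592 group.

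The error is selective. Placebo responders and the efavaleukin arms keep their treatment (Protocol Table 6-1), so only placebo nonresponders can be relabelled, all into the one dose group used for the switch. Antibody tables are affected only if they use the induction label; SAP Sections 6.5 and 9.6.6 name no period.

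**Working it through.** No power or sample size figure is involved. The check applies the date rules to example subjects.

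**Inputs.** Week 12 visit on day 85 ± 5 (Protocol Table 1-2). Placebo on days 1, 15, …, 71 is an assumption taken from the 14-day window in the SAP exposure definitions, because the dosing frequency is blacked out. The first efavaleukin dose follows the endoscopy.

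**Rules.** Label: efavaleukin if any efavaleukin dose falls on or before the end of induction date. Induction exposure: earliest of last dose before endoscopy + 13 and first dose after endoscopy − 1 (end of study and data cutoff are later here), minus day 1, plus 1. Induction adverse event window: ends at min[end of study, 90, max(week 12 dose date − 1, endoscopy date)].

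| Endoscopy day | First efavaleukin dose | Induction label | Induction exposure (days) | Event window ends |
|---|---|---|---|---|
| 85 | 85 | efavaleukin | 84 | 85 |
| 85 | 86 | placebo | 84 | 85 |
| 85 | 88 | placebo | 84 | 87 |
| 80 | 80 | efavaleukin | 79 | 80 |
| 90 | 90 | efavaleukin | 84 | 90 |

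- First row: 71 + 13 = 84, and 84 − 1 + 1 = 84 days, all placebo. One definition calls the period placebo-only and the other calls it efavaleukin. The 79 in the fourth row treats the same-day dose as after the endoscopy (80 − 1 = 79).
- Calendar days before the dose: 85 − 1 = 84, or 79 to 89 across the visit window.
- In the day 1 to 85 event window, 84/85 = 98.8% of days precede the efavaleukin dose.
- Overall rates, if the subject is followed to day 365: 84/365 = 23.0% of person-time is placebo time credited to efavaleukin. Earlier end of study makes the share larger.

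**No week 12 endoscopy.** The cut-off becomes min(day 90, end of study), so an efavaleukin dose on day 85 also sets the label. Here the induction exposure definition falls back on the last dose before end of study, so the clash with it is confined to the same-day case. Protocol Section 4.1.2 expects week 12 evaluations to be complete before long-term treatment, so this case should be uncommon.

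**Long-term exposure.** This duration is computed "minus the day of first IP administration after the" endoscopy, with a word blacked out before endoscopy. Assume a last dose on day 351 (351 + 13 = 364). If a same-day dose counts as after the endoscopy, the duration is 364 − 85 + 1 = 280, and 84 + 280 = 364. If *after* means a later date, the start is day 99: 364 − 99 + 1 = 266, and 84 + 266 = 350, which leaves 14 days in neither period.

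**The case against.** The strongest objection is that nothing shows the case occurs. The dosing window exists to permit a separate day, and the blacked-out text beside it may add conditions. That stands: the documents support only that same-day dosing is permitted.

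Second, the intent is visible. The long-term definition takes product from week 12, the overall groups name placebo followed by AMG 592, the exposure definition stops before the endoscopy, and Protocol Table 6-1 puts the week 12 dose in the long-term period. The start date in SAP Section 5.3 and the Appendix B windows could be read as placing periods and evaluations, not doses. This shows what was meant, but the label rule refers to the end of induction date by name and would be programmed as written.

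Four stronger readings are tempting and are not supported:

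- *The SAP foresaw same-day dosing, because its adverse event window includes the endoscopy date.* That term is also needed for every subject who does not continue and so has no week 12 dose.
- *A sizeable part of the placebo arm would move.* The nonresponse, continuation and same-day shares are not given, and 60 per arm is planned enrolment, before the termination in SAP Section 11 and the exclusion of one site. No arm-level figure can be derived.
- *Long-term exposure loses 14 days.* This depends on reading *after* by date, beside a blacked-out word. Read by time of day, the periods add up exactly.
- *Any dose after the endoscopy day is always labelled correctly.* This fails to cover subjects with no week 12 endoscopy.

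**Conclusion.** The label rule gives the wrong answer for a placebo nonresponder whose first efavaleukin dose falls on the week 12 endoscopy day, or by min(day 90, end of study) when there is no week 12 endoscopy. In the same-day case it contradicts the SAP's own induction exposure definition and can remove the subject from the overall group meant for that sequence.

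For each affected subject, about 84 placebo days carry an efavaleukin label, given 14-day dosing and a day 85 visit. The 23% share of overall person-time also assumes follow-up to day 365; it is an illustration, not a bound, because the trial was terminated early.

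The effect is limited to descriptive analyses by actual treatment. Efficacy uses randomized treatment in the full analysis set and does not change. The number affected may be zero, and the direction of any bias cannot be determined from the documents. The conflict in the definitions is certain and its consequence is not. Since treatment-emergent adverse events are a secondary endpoint of a dose-finding trial, and the repair is small, it should be fixed.

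**What to change.** Use one cut-off, the first long-term (week 12) dose, throughout SAP Section 5.1:

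- **Actual treatment in induction:** count only product given before the first long-term dose, or up to the end of induction date if no long-term dose is given. This also covers subjects with no week 12 endoscopy.
- **Actual treatment in the long-term period:** start the label at that dose.
- **Induction and long-term exposure:** state that a week 12 dose on the endoscopy day is long-term product, so induction exposure ends the day before it and long-term exposure starts on it.
- **Induction adverse event window:** for subjects dosed on the endoscopy day, either align the end of the window with the new cut-off, or keep it and add a footnote and a listing of events with onset on that date. If only the label changes, post-dose reactions that day would be tabulated under placebo without notice. Protocol Section 11.4 lists onset dates among the required event attributes, not times, so events that day cannot be fully separated from the listed attributes.
- **Section 5.3 and Appendix B:** leave these as evaluation windows, and say that they do not decide which period a dose belongs to.

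The cost is a few sentences, one derivation change and at most one footnote and listing. The adverse event window already uses a week 12 dose date, so the variable exists. No dosing rule changes.
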